6.7 TREATMENT PERIOD

6.8 DAY 1 - ARM A ONLY

The following must be performed on Day 1 prior to dose of cabozantinib:

- Interval history
- Physical examination including major body systems. The Day 1 physical examination does not need to be performed if the screening physical examination was performed within 7 days of the Day 1 visit.
- Karnofsky Performance Status (KPS), body weight, and vital signs (temperature, blood pressure, heart rate, respiratory rate). The Day 1 KPS evaluation does not need to be performed if the screening KPS evaluation was performed within 7 days of the Day 1 visit.
- Assessment of concomitant medications, toxicities and treatments
- Dispense study drug to the patient
- Sample collection for the following laboratory evaluations if not done for screening with 7 days:
 - Complete blood count (CBC) with differential: WBC count with differential, platelet count, hemoglobin, and hematocrit.
 - Serum chemistries: Sodium, potassium, chloride, blood urea nitrogen (BUN) or urea, creatinine, glucose, carbon dioxide (CO₂) or bicarbonate, aspartate aminotransferase (AST), alanine aminotransferase (ALT), albumin, total bilirubin, alkaline phosphatase, LDH.
 - Urine protein creatinine ratio
 - PSA level
 - Thyroid function testing: TSH and T4.

6.9 DAY 15 - ARM A ONLY

The following must be performed on Day 15:

- Interval history
- Physical examination including major body systems.

- Karnofsky Performance Status (KPS), body weight, and vital signs (temperature, blood pressure, heart rate, respiratory rate)
- Sample collection for the following laboratory evaluations:
 - Complete blood count (CBC) with differential: WBC count with differential, platelet count, hemoglobin, and hematocrit.
 - Serum chemistries: Sodium, potassium, chloride, blood urea nitrogen (BUN) or urea, creatinine, glucose, carbon dioxide (CO₂) or bicarbonate, aspartate aminotransferase (AST), alanine aminotransferase (ALT), albumin, total bilirubin, alkaline phosphatase, LDH.
 - Urine protein creatinine ratio
- Assessment of concomitant medications, toxicities and treatments

6.10 DAY 29 - ARM A ONLY

The following procedures must be performed on Day 29:

- Interval history
- Physical examination including major body systems
- Karnofsky Performance Status (KPS), body weight, and vital signs
- Sample collection for the following laboratory evaluations:
 - Complete blood count (CBC) with differential: WBC count with differential, platelet count, hemoglobin, and hematocrit.
 - Serum chemistries: Sodium, potassium, chloride, blood urea nitrogen (BUN) or urea, creatinine, glucose, carbon dioxide (CO₂) or bicarbonate, aspartate aminotransferase (AST), alanine aminotransferase (ALT), albumin, total bilirubin, alkaline phosphatase, LDH.
 - Urine protein creatinine ratio
 - PSA level
 - Testosterone level
 - Thyroid function testing: TSH and T4.
- Assessment of concomitant medications, toxicities and treatments
- Plasma/serum biomarker studies

6.11 DAY 43 - ARM A ONLY

The following procedures must be performed on Day 43:

- Prostatectomy
- Tissue procurement at the time of surgery for pathologic and research assessments.

6.12 DAY 50 - ARM A ONLY

The following procedures must be performed on Day 50:

- Interval history
- Physical examination including major body systems
- Karnofsky Performance Status (KPS), body weight, and vital signs

- Sample collection for the following laboratory evaluations:
 - Complete blood count (CBC) with differential: WBC count with differential, platelet count, hemoglobin, and hematocrit.
 - Serum chemistries: Sodium, potassium, chloride, blood urea nitrogen (BUN) or urea, creatinine, glucose, carbon dioxide (CO₂) or bicarbonate, aspartate aminotransferase (AST), alanine aminotransferase (ALT), albumin, total bilirubin, alkaline phosphatase, LDH.
 - Urine protein creatinine ratio
- Assessment of concomitant medications, toxicities and treatments

6.13 SAFETY FOLLOW UP VISIT - ARM A ONLY

At the post-surgery follow-up visit, the following procedures should be performed:

- Interval history (to include review of hospital course while patient underwent prostatectomy)
- Assessment of any adverse events and tumor-related signs and symptoms
- Physical examination including major body systems
- Karnofsky Performance Status (KPS), body weight, and vital signs and other tests as necessary to follow unresolved or evaluate new adverse events
- Sample collection for the following laboratory evaluations:
 - Complete blood count (CBC) with differential: WBC count with differential, platelet count, hemoglobin, and hematocrit.
 - Serum chemistries: Sodium, potassium, chloride, blood urea nitrogen (BUN) or urea, creatinine, glucose, carbon dioxide (CO₂) or bicarbonate, aspartate aminotransferase (AST), alanine aminotransferase (ALT), albumin, total bilirubin, alkaline phosphatase, LDH.
 - Urine protein creatinine ratio
 - PSA level
 - Testosterone level
 - Thyroid function testing: TSH and T4. Thyroid function tests (TFTs) will be performed only for subjects who require clinical intervention due to alteration in TFTs at an earlier time point.
- Assessment of concomitant medications, toxicities and treatments
- Plasma/serum biomarker studies
- For extraordinary responders we will obtain archival tissue from their prostate biopsy pre prostatectomy

6.14 DAY 1 - ARM B ONLY

The following procedures must be performed on Day 1:

- Prostatectomy
- Tissue procurement at the time of surgery for pathologic and research assessments

6.15 RELAPSE FREE SURVIVAL FOLLOW UP PERIOD

Arm A and Arm B subjects will be followed for relapse free survival for 3 years from date of prostatectomy. Follow up will occur every 3 months (+/- 1 month). Follow up may be obtained by a phone call, clinic visit or chart review.

6.16 END OF STUDY

Reasons to discontinue the subject prior to 3 years include: biochemical progression, disease progression, new treatment for prostate cancer, withdrawal, or death. This determination may require obtaining outside records and interpretation by the investigator.

7 STUDY INTERVENTION

7.1 COMPOSITION, FORMULATION, AND STORAGE

At study sites, all study medication will be stored as described in the appropriate prescribing information and inventoried in accordance with applicable state and federal regulations.

7.2 INVESTIGATIONAL TREATMENT: CABOZANTINIB

Cabozantinib tablets are supplied as film-coated tablets containing cabozantinib malate equivalent to 20 mg and contain microcrystalline cellulose, lactose anhydrous, hydroxypropyl cellulose, croscarmellose sodium, colloidal silicon dioxide, magnesium stearate and Opadry® yellow. The 20-mg tablets are round. Doses of 40 mg will comprise two 20-mg tablets. The components of the tablets are listed in **Table 7-1**.

Table 7-1: Cabozantinib Tablet Components and Composition

Ingredient	Function	% w/w ^a
Cabozantinib Drug Substance (25% drug load as free base)	Active Ingredient	31.68
Microcrystalline Cellulose (Avicel® PH-102)	Filler	38.85
Lactose Anhydrous (60M)	Filler	19.42
Hydroxypropyl Cellulose (EXF)	Binder	3.00
Croscarmellose Sodium (Ac-Di-Sol®)	Disintegrant	6.00
Colloidal Silicon Dioxide	Glidant	0.30
Magnesium Stearate	Lubricant	0.75
Opadry® yellow film coating which includes HPMC 2910/hypromellose 6 cp, titanium dioxide, triacetin, and iron oxide yellow	Film Coating	4.00

^a weight fraction, expressed in percentage; HPMC, hydroxypropyl methylcellulose

7.3 CABOZANTINIB ADMINISTRATION

Subjects will receive cabozantinib orally at a (starting) dose of 40 mg once daily. Study drug will be provided by Exelixis. Study drug should at all times be kept in the original packaging. Study drug will be

dispensed directly in clinic and returned at the end of 28 days. Cabozantinib will be supplied as 20 mg tablets in bottles of 30 tablets. Subjects will be given two bottles for their 28 day dosing. Doses of 40 mg will comprise two 20 mg tablets. A pill diary will be provided to keep accurate information on drug administration and any notes that the subject adds to the diary.

Cabozantinib must be taken on an empty stomach. Subjects must be instructed not to eat for at least 2 hours before and at least 1 hour after taking cabozantinib. Subjects should be instructed to take their cabozantinib dose at approximately the same time every day. If a subject misses a dose, the dose may be taken later only if it is within 12 hours of when the missed dose should have been taken. The missed dose should not be made up if it is within 12 hours of the next scheduled dose.

Cabozantinib tablets should be swallowed whole with at least 8 ounces of water. The tablets should not be crushed. Grapefruit, grapefruit juice, Seville oranges and their products should be avoided by subjects taking cabozantinib.

In all subjects, dose reductions and delays to manage toxicity are allowed under the guidelines in Table 7.3

7.4 CABOZANTINIB DOSE MODIFICATIONS, INTERRUPTIONS, AND DISCONTINUATION

The following should be taken into consideration in decisions regarding dose modifications (reductions or interruption):

- As a general approach all AEs should be managed with supportive care at the earliest signs of toxicity considered related to the study treatment. Should this be ineffective, dose interruptions and/or reductions should be considered to prevent worsening of toxicity.
- The assigned starting dose for cabozantinib is 40 mg/day. One dose reduction level of cabozantinib to 20 mg/day is permitted (see Table 7-2).
- Dose modification criteria for cabozantinib are shown in Table 7-3. Dose interruptions and/or reductions should be implemented for unacceptable toxicity. Doses may be modified at any time while a subject is on treatment.
- Dose reductions or interruptions may also occur in the setting of lower grade toxicity than defined in Table 7-3, if the investigator feels it is in the interest of a subject's safety and will optimize drug tolerability.
- Interruption of cabozantinib treatment for cabozantinib-related AEs may occur at any time per investigator discretion. If treatment is interrupted due to related AEs for more than 1 week, cabozantinib should be discontinued unless there is unequivocal evidence that the subject is benefitting. In this situation, a subject may be able to restart therapy with a dose reduction upon resolution of the toxicity per the discretion of the investigator.

Guidelines for the management of specific AEs are provided in Section 7.4.2.

Table 7-2: Dose Reductions of Cabozantinib

Assigned Dose	First Dose Level Reduction	Second Dose Level Reduction
40-mg cabozantinib oral qd	20-mg cabozantinib oral qd	No dose reduction permitted

Cabozantinib will be discontinued if a daily dose of 20-mg cabozantinib (minimum dose) is not tolerated

Table 7-3: Dose Modifications of Cabozantinib for Treatment-Related AEs

CTCAE v.5.0 Grade	Recommended Guidelines for Management ^a
Grade 1 AEs	Add supportive care as indicated. Continue cabozantinib treatment at the current dose level if AE is manageable and tolerable.
Grade 2 AEs which are tolerable and are easily managed	Continue cabozantinib treatment at the current dose level with supportive care.
Grade 2 AEs which are intolerable and cannot be adequately managed	At the discretion of the investigator, cabozantinib should be dose reduced or interrupted. Note: It is recommended that dose holds be as brief as possible.
Grade 3 AEs (except clinically non-relevant laboratory abnormalities)	Cabozantinib should be interrupted unless the toxicity can be easily managed with a dose reduction and optimal medical care. Note: It is recommended that dose holds be as brief as possible.
Grade 4 AEs (except clinically non-relevant laboratory abnormalities)	Subjects should have cabozantinib interrupted immediately. Discontinue cabozantinib unless the following criteria are met: 
 • Subject is deriving clear clinical benefit as determined by the investigator • Toxicity can be managed with a dose reduction following recovery to Grade 1 (or baseline) and optimal medical care

Note: The dose delay and modification criteria for specific medical conditions are provided in Section 7.4.2 For re-treatment criteria of study treatment after a dose hold see Section 7.4.1.

^aStudy treatment dose adjustment is only needed if the toxicity was deemed related to cabozantinib treatment or had an unclear relationship to cabozantinib treatment.

7.4.1 CABOZANTINIB DOSE REINSTITUTION AND REESCALATION

If the subject recovers from his or her toxicities to CTCAE v.5.0 Grade ≤ 1 or to the baseline value (or lower) and the toxicity was unrelated to study treatment, then study treatment may be restarted with no change in dose.

If the subject recovers from his or her toxicities to Grade ≤ 1 or to the baseline value (or lower) the toxicity was deemed possibly related to study treatment, then study treatment may be restarted at a reduced dose (see Table 7-2 for the schedule of dose reductions).

Subjects receiving a daily dose of 20 mg may be restarted at the same dose if deemed safe at the discretion of the investigator. Subjects unable to tolerate a daily dose of 20 mg should discontinue study treatment.

Re-escalation to the previous dose, (but not higher than 40 mg/day) may be allowed at the discretion of the investigator for AEs which have resolved or recovered to Grade 1 (or baseline value) and deemed tolerable and easily managed by optimized supportive treatment. Dose re escalation is not allowed for a drug-related dose reduction triggered by Grade 4 hematologic toxicities or by Grade 4 AEs affecting major organs (e.g., central nervous system, cardiac, hepatic, renal).

7.4.2 GUIDELINES FOR MANAGEMENT OF POTENTIAL ADVERSE EVENTS

Subjects on Arm A receiving cabozantinib will be monitored for AEs from the time of taking the first dose of study drug through their last follow-up visit (30 days after the date of the last dose of cabozantinib treatment). Subjects will be instructed to notify their physician immediately at the onset of any AE. Seriousness, severity grade, and relationship to study treatment of AEs will be determined by the investigator. AE severity will be graded by the investigator in accordance with CTCAE v.5.0.

Management of severe or intolerable adverse reactions may require temporary dose reduction and/or interruption for cabozantinib.

7.4.2.1 CABOZANTINIB

The most frequent AEs experienced by $\geq 20\%$ of subjects treated with cabozantinib in descending order of frequency were diarrhea, fatigue, decreased appetite, nausea, weight decreased, PPES, vomiting, constipation, hypertension, dysgeusia, dysphonia, asthenia, and dyspnea. For a full description of the safety profile of cabozantinib, refer to the Cabozantinib Investigator's Brochure.

Other medically important but less frequent AEs including arterial thrombotic AEs (e.g., transient ischemic attack [TIA], and myocardial infarction [MI]) and venous thrombotic AEs (e.g., deep vein thrombosis [DVT] and pulmonary embolism), severe hemorrhagic events, proteinuria, wound healing complications, gastrointestinal (GI) perforation, abscesses including intra-abdominal and pelvic abscess, GI and non-GI fistula formation, osteonecrosis, and reversible posterior leukoencephalopathy syndrome (RPLS).

Adverse events associated with laboratory abnormalities experienced by $\geq 5\%$ of subjects treated with cabozantinib in descending order of frequency were anemia, AST increased, ALT increased, hypothyroidism, hypokalemia, hypomagnesemia, thrombocytopenia, hypocalcemia, hypophosphatemia, lactate dehydrogenase (LDH) increased, lipase increased, neutropenia, hyponatremia, ALP increased, leukopenia, and hyperglycemia.

Adverse events may occur within the first few weeks in the course of treatment with cabozantinib, as cabozantinib is expected to reach steady state exposure at approximately 2 weeks following first dose. Events that generally have an early onset include hypocalcemia, hypokalemia, thrombocytopenia, hypertension, PPES, abdominal pain, mucosal inflammation, constipation, diarrhea, and vomiting. Adverse events should be managed with supportive care at the earliest signs of toxicity. Dose reductions and treatment interruptions should be considered. Dose reductions are recommended for events that, if persistent, could become serious or intolerable (Section 7.3).

Cabozantinib should be discontinued for the following AEs: visceral perforation or fistula formation, severe hemorrhage, serious arterial thromboembolic events, nephrotic syndrome, hypertensive emergency, persistent uncontrolled hypertension despite optimal medical management, and RPLS.

7.4.2.2 GASTROINTESTINAL DISORDERS

Gastrointestinal perforation, GI fistula, and intra-abdominal and pelvic abscess: After starting treatment with cabozantinib, subjects should be monitored for early signs of GI perforation such as abdominal pain, nausea, emesis, constipation, and fever especially if known risk factors for developing GI perforation or fistula (Turnage and Badgwell 2016) are present. Discontinue cabozantinib and initiate appropriate management in subjects who have been diagnosed with GI perforation or fistula.

Diarrhea: Subjects should be instructed to notify their physician immediately at the first signs of poorly formed or loose stool or an increased frequency of bowel movements. Guidelines for the evaluation and management of diarrhea are shown in **Table 7-4**. Administration of antidiarrheal/antimotility agents is recommended at the first sign of diarrhea as initial management. Some subjects may require concomitant treatment with more than one antidiarrheal agent. When therapy with antidiarrheal agents does not control the diarrhea to tolerable levels, cabozantinib should be temporarily interrupted or dose reduced. When the diarrhea is controlled, retreatment with cabozantinib may be acceptable per investigator decision. In addition, general supportive measures should be implemented such as continuous oral isotonic hydration, correction of fluid and electrolyte abnormalities, small frequent meals, and stopping lactose-containing products, high-fat meals, and alcohol.

Recurrent or prolonged diarrhea can be associated with anal or perianal skin erosions which increase the risk for anal abscesses, fistulas, or proctitis. Good personal hygiene should be emphasized. Regular examinations of the perianal region should be performed whenever diarrhea has occurred during treatment with cabozantinib. Infections of the perianal region should be treated per local guidelines.

Table 7-4: Management of Diarrhea Associated with Cabozantinib

Status	Management
Tolerable Grade 1-2 (duration < 48 h)	
 • Continue with study treatment and consider dose reduction • Initiate treatment with an antidiarrheal agent (e.g., loperamide 4 mg followed by 2 mg after each episode of diarrhea [maximum: 16 mg loperamide per day]) • Dietary modifications (e.g., small lactose-free meals, bananas and rice) • Intake of isotonic fluids (1-1.5 L/day) • Re-assess after 24 hours: 
 ○ Diarrhea resolving to baseline bowel habits: gradually add solid foods and discontinue or decrease antidiarrheal treatment after 12 h diarrhea-free interval ○ Diarrhea not resolving: Continue/resume antidiarrheal treatment
Intolerable Grade 2, Grade 2 > 48 h, or ≥ Grade 3	
 • Interrupt study treatment • Ask subject to attend clinic • Rule out infection (e.g., stool sample for culture) 
 ○ Administer antibiotics as needed (e.g., if fever or Grade 3-4 neutropenia persists > 24 h) • Administer fluids (1-1.5 L/day orally or IV, as appropriate) for hydration or to correct electrolyte abnormalities • For Grade 3-4 or complicated lower grade diarrhea consider hospitalization and IV hydration • Re-assess after 24 h 
 ○ Diarrhea resolving to baseline bowel habits or Grade ≤ 1: consider restarting study treatment at reduced dose ○ Diarrhea not resolving: Start and or continue antidiarrheal treatment (e.g., loperamide 4 mg followed by 2 mg after each episode of diarrhea [maximum: 16 mg loperamide per day]). Consider starting second line antidiarrheal or referral to gastroenterologist

Nausea and vomiting: Antiemetic agents are recommended as clinically appropriate for treatment or prophylaxis of nausea and vomiting, along with supportive care. Dehydration and electrolyte abnormalities may be associated with vomiting and monitoring for and correction of fluid and electrolyte disturbances should be implemented. Antiemetic medications should be assessed for potential drug interactions (refer to Section 8.2 for further details).

Dehydration: Dehydration events have been identified with comparable incidence and occurring in a shorter time to onset in the prostate cancer studies than previously experienced with cabozantinib in other tumor types. Extra monitoring/medical management including electrolyte monitoring and/or early dose reduction of patients exhibiting dehydration symptoms and those with risk factors for dehydration is indicated.

7.4.2.3 NON-GASTROINTESTINAL FISTULA

Complications from radiation therapy especially of the thoracic cavity including mediastinum have been identified as a possible predisposing risk factor for non-GI fistula formation in subjects undergoing treatment with VEGF pathway inhibitors.

Discontinue cabozantinib and initiate appropriate management in subjects who have been diagnosed with a non-GI fistula.

7.4.2.4 HEMORRHAGE

Hemorrhagic events, including serious and sometimes fatal events, have been reported with cabozantinib. Subjects should be monitored for bleeding events with serial complete blood counts and physical examination while on study. The risk of hemorrhage in cabozantinib-treated subjects with brain metastases has not been thoroughly analyzed. Subjects enrolled with treated and stable brain metastases should be monitored with a high index of suspicion if symptoms that could be due to a CNS hemorrhage occur.

Cabozantinib should be discontinued in subjects with serious and life-threatening bleeding events or recent hemoptysis (≥ 2.5 mL of red blood).

7.4.2.5 THROMBOEMBOLIC EVENTS

Thromboembolic events are frequent in cancer subjects due to procoagulant changes induced by the malignancy or anticancer therapy. DVT and pulmonary embolism have been observed in clinical studies with cabozantinib, including fatal events. Subjects who develop a pulmonary embolism and/or DVT should have study treatment interrupted until therapeutic anticoagulation is established. Treatment with cabozantinib may be resumed in subjects with pulmonary embolism or DVT if it is determined that the event is uncomplicated and that the subject is deriving clinical benefit from cabozantinib treatment and that anticoagulation does not place them at a significant risk that outweighs the benefit of resuming treatment per discretion of the investigator and according to individual protocols. Low molecular weight heparins are the preferred management for thrombotic events; oral anticoagulants (e.g., warfarin or other coumarin-related agents, direct thrombin or direct FXa inhibitors, or antiplatelet agents, or chronic use of aspirin above low dose levels for cardioprotection per local applicable guidelines) are not allowed.

Arterial thrombotic events (e.g., TIA, MI) have been observed in studies with cabozantinib. Further treatment with cabozantinib should be discontinued in subjects who develop an acute MI, cerebral infarction, or any other clinically significant arterial thromboembolic complication.

7.4.2.6 HYPERTENSION

Table 7-5 provides treatment guidelines for hypertension deemed related to cabozantinib. Blood pressure should be monitored in a constant position visit to visit, either sitting or supine in a relaxed setting. Decisions to reduce or interrupt the dose of study treatment must be based on BP readings taken by a medical professional and must be confirmed with a second measurement at least 5 minutes following the first measurement.

Cabozantinib should be discontinued in subjects with hypertensive emergency.

Table 7-5: Management of Hypertension Associated with Cabozantinib

Criteria for Dose Modifications	Treatment/Cabozantinib Dose Modification
Subjects NOT receiving optimized anti-hypertensive therapy	
> 150 mm Hg (systolic) ^a and < 160 mm Hg OR > 100 mm Hg (diastolic) and < 110 mm Hg	
 Optimize antihypertensive medications by adding new or additional antihypertensive medications and/or increase dose of existing medications. Reduce cabozantinib treatment by one dose level if optimal antihypertensive therapy (usually to include 3 agents) does not result in BP <150 mm Hg systolic or <100 mm Hg diastolic If subject is symptomatic interrupt cabozantinib treatment
≥ 160 mm Hg (systolic) OR ≥ 110 mm Hg (diastolic)	
 Reduce cabozantinib by one dose level^b or interrupt cabozantinib treatment per investigator discretion Add new or additional anti-hypertensive medications and/or increase dose of existing medications and monitor subject closely for hypotension. If optimized antihypertensive therapy (usually to include 3 agents) does not result in BP < 150 mm Hg systolic or < 100 mm Hg diastolic, cabozantinib treatment should be dose reduced further or interrupted Cabozantinib treatment should be dose interrupted if upper limits of systolic BP (≥ 160 mm Hg) are sustained and not adequately manageable or if systolic BP is > 180 mm Hg or diastolic BP > 110 mm Hg, or if subject is symptomatic Re-start cabozantinib treatment at the most tolerable dose and re-escalate only if BP falls to and is sustained at < 150 mm Hg systolic and < 100 mm Hg diastolic
Hypertensive emergency ^c	
 Discontinue cabozantinib treatment

BP, blood pressure.

^a The investigator may decide to initiate or adjust antihypertensive treatment at a lower threshold than systolic BP >150 or diastolic BP >100 based on their clinical judgment and assessment of the individual subject.

^b Permitted dose levels are defined by individual protocols.

^c Hypertensive emergency is defined as uncontrolled elevated BP with clinical evidence of progressive or impending end-organ damage (e.g., myocardial infarction/ischemia, intracranial hemorrhage, cerebral ischemia, pulmonary edema, encephalopathy, kidney damage).

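### Table 7-5 states the blood-pressure target with *or* where its own re-escalation rule uses *and*, so the dose-reduction instruction is ambiguous for a man with only one component controlled

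*Combined protocol and SAP*

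**What the plan says.** Section 7.4.2.6 gives the hypertension rules in Table 7-5. A man enters the first row if his systolic pressure is above 150 and below 160 mm Hg, or his diastolic is above 100 and below 110. His medication is then optimized, usually to about three agents. Cabozantinib is reduced one level if this "does not result in BP <150 mm Hg systolic or <100 mm Hg diastolic". Symptomatic men are interrupted.

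The second row (systolic 160 or more, or diastolic 110 or more) begins with a one-level reduction or an interruption. It repeats the same *or* target and says that, if the target is missed, "cabozantinib treatment should be dose reduced further or interrupted". It allows re-escalation only if "BP falls to and is sustained at < 150 mm Hg systolic and < 100 mm Hg diastolic".

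Section 7.4 and Table 7-2 permit one reduction, from 40 to 20 mg daily, and none below that. Footnote b of Table 7-5 reads "Permitted dose levels are defined by individual protocols".

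On stopping for good, Section 7.4.2.1 lists hypertensive emergency and, as a separate item, "persistent uncontrolled hypertension despite optimal medical management, and RPLS". The text above Table 7-5 names only the first: "Cabozantinib should be discontinued in subjects with hypertensive emergency". The last row of the table does the same.

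**The concern.** The row is entered on either component, but the target is worded so that controlling either component appears to be enough. The table asks for both components when the dose goes back up. A site that follows the reduction line to the letter could leave a man at 40 mg with a pressure that the table itself treats as too high for re-escalation.

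This is a safety instruction for a drug known to raise blood pressure. Section 7.4.2.1 lists hypertension among the early-onset events, and treatment lasts only 28 days. The note under Table 7-3 sends sites to Section 7.4.2 for condition-specific criteria, so Table 7-5 is the rule they will consult.

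Two smaller mismatches sit in the same place. A further reduction does not exist for a man already at 20 mg. The table also omits one of the two hypertension-related reasons for discontinuation in Section 7.4.2.1.

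**Working it through.** The plan states no figure on this point, so there is none to reproduce. The check is one of logic, followed by a bound on exposure.

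**1. The target line.** Let S and D be systolic and diastolic pressure on optimized therapy.

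- Literal *or* target: reduce if NOT (S < 150 or D < 100), that is, only if S ≥ 150 and D ≥ 100.
- *And* target: reduce if NOT (S < 150 and D < 100), that is, if S ≥ 150 or D ≥ 100.

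| Reading | In first row? | Reduce, literal *or* | Reduce, *and* | Meets re-escalation target? |
|---|---|---|---|---|
| 155/95 | yes | no | yes | no |
| 145/108 | yes | no | yes | no |
| 155/105 | yes | yes | yes | no |
| 145/95 | no | no | no | yes |

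A first-row man can be uncontrolled in three ways: systolic only, diastolic only, or both. The literal wording reduces in one of the three and the *and* wording in all three. These are logical states, not proportions of men.

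**2. Second row.** These men are reduced or interrupted on entry. Interruption is also called for if systolic pressure of 160 or more is sustained and not manageable, if systolic exceeds 180 or diastolic exceeds 110, or if the man is symptomatic. The *or* therefore matters much less here.

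**3. Dose ladder.** 40 mg, then 20 mg, then none (Table 7-2). A further reduction is unavailable to a man who took the reduction branch. A man who was interrupted at 40 mg still has one level left.

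**4. Exposure if acted on at scheduled visits.** Inputs: 28 daily doses of 40 mg from Day 1 (Section 7.3); vital signs at Day 15 ± 3 and Day 29 ± 3 (Section 6.1, Arm A); dose decisions based on readings by a medical professional (Section 7.4.2.6). Both rows sit under the heading for men not yet on optimized therapy.

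- Planned total: 28 × 40 = 1,120 mg.
- A first-row man found at Day 15 has his medication optimized first under either wording. The *or* matters only at a later reading.
- The next scheduled reading can fall as early as Day 26. Doses left, including that day: 28 − 26 + 1 = 3.
- Excess at 40 rather than 20 mg: 3 × 20 = 60 mg; 60 / 1,120 = 5.4%.
- If that visit falls on Day 29 or later, no doses remain and the excess is zero.

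**5. Exposure if therapy is already optimized by Day 15 (assumption).**

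- Doses left at Day 15: 28 − 15 + 1 = 14 (17 at Day 12; 11 at Day 18).
- Excess: 14 × 20 = 280 mg (220 to 340 mg), or 25% (20% to 30%) of 1,120 mg.

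The documents give no rate for this case, or for unscheduled readings between the visits.

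**The case against.** The strongest reply is that the literal reading is not the intended one. Because the row is entered on either component, the target line can be read as telling the site to reduce if either limit is missed. Under the literal reading, a man with an isolated systolic rise and diastolic below 100 meets the target before any treatment, which is absurd and counts against that reading. This stands, and it is why the defect is an ambiguity rather than a rule certain to mis-dose. It does not remove the case for an edit, because the same table uses *and* for the same pair of limits.

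A second reply is that other text acts on this man. Section 7.4 lets the investigator modify the dose at any time, and Section 7.4.2.1 discontinues persistent uncontrolled hypertension whether or not the table repeats it. This also stands. A reader might infer that the table keeps such a man on 40 mg; the protocol as a whole does not.

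A reader might also take 25% extra exposure as the size of the problem. That needs therapy already optimized by Day 15, or unscheduled readings that bring the decision forward to that point, and the documents support neither as typical.

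Nor is the mention of a further reduction a dead end, since the same sentence offers interruption. The missing discontinuation item leaves no large hole either. Section 7.4 adds "If treatment is interrupted due to related AEs for more than 1 week, cabozantinib should be discontinued unless there is unequivocal evidence" that the man is benefitting, discontinues if 20 mg is not tolerated, and Section 7.4.1 ties restart after a related toxicity to recovery.

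**Conclusion.** The inconsistency between the target lines and the re-escalation line is real, and it bears on a safety rule. Taken literally, the target lines spare a first-row man a dose reduction when only one component is controlled. Whether any site would read them so cannot be known from the documents.

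The number of men affected cannot be estimated. No rate of hypertension refractory to optimized therapy at 40 mg is given, and exclusion criterion 10 removes men whose hypertension medication cannot control. The 60 mg (about 5%) bound assumes uninterrupted dosing from Day 1 and dose decisions made only at scheduled visits; it could be larger only with unscheduled readings or therapy already optimized by Day 15.

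The wording on further reduction, together with footnote b, looks like generic text not adapted to this protocol. The discontinuation mismatch is a matter of making the table agree with a rule that already binds. Severity is minor.

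**What to change.** 1. In both blood-pressure rows of Table 7-5, change *or* to *and* in the target line, so that it matches the re-escalation line.
2. As tidying, replace the second-row instruction on further reduction with: reduce to 20 mg if not already reduced (Table 7-2), otherwise interrupt.
3. Optionally, add the persistent-hypertension item to the discontinuation row and to the sentence above the table, in the exact words of Section 7.4.2.1 (the quoted text up to, but not including, RPLS). Do not add a condition that reduction or interruption under Section 7.4 must come first: Section 7.4.2.1 has none, so the condition would narrow the existing rule and create a new conflict.

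The cost is text edits to one table and one sentence, with no added patients, visits or procedures. A few men may move to 20 mg earlier. They stay evaluable, because Section 4.5 counts days of dosing rather than dose level.
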